In Phase II, for participants randomized to the treatment arm, if the participant does not complete the post-intervention assessments within 2 weeks from the end of the intervention period they will be considered lost to follow up. If a participant chooses to withdraw from the study at any point or the participant is deemed lost to follow up or is dropped from the study during the intervention period (5 weeks), access to the web portal and mobile app will be restricted at that time, otherwise access to the mobile app will be restricted at the end of the intervention period and access to the web portal will be restricted after post-intervention assessments have been completed or the participant is deemed lost to follow up (2 weeks after intervention period).

Participants randomized to the control arm will have two weeks to complete the post-intervention assessments. Once the post-intervention assessments have been completed or 2 weeks have passed, whichever occurs first, participants in the control arm will be granted access to the treatment condition (Limbix Spark) for 5 weeks. After access to Limbix Spark for 5 weeks, participants will have two weeks to complete another set of post-intervention assessments. If a participant chooses to withdraw from the study or the participant is deemed lost to follow up during the control app intervention period or Limbix Spark app intervention period (5 weeks

each), access to the web portal and mobile app will be restricted at that time. Otherwise, access to the mobile app will be restricted at the end of each intervention period and access to the web portal will be restricted after the second set of post-intervention assessments have been completed or the participant is deemed lost to follow up (2 weeks after Limbix Spark intervention period).

In Phase II, if participants report a change in their treatment for a mental health disorder while enrolled in the study, they may be withdrawn from the study.

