## Phase II

The main purpose of Phase II is to evaluate the effectiveness of the Limbix Spark program relative to an educational control condition. All analyses will be restricted to those participants with PHQ-8  $\geq 10$  unless otherwise indicated. Data from participants who reported a change in their medication or treatment for a mental health disorder that occurred during the study may be excluded from primary analysis. The core analysis strategy in this project is longitudinal mixed effects modeling, where we fully utilize the repeatedly measured primary and secondary outcomes and maximum likelihood estimation will be applied.

Data across versions 2 and 3 will be pooled and statistical analyses conducted with the combined dataset may be computed with version included as a covariate. Statistical analyses may also be conducted separately for versions 2 and 3 cohorts. All analyses will be completed in line with the intent-to-treat (ITT) principle, where all participants will be included in the analyses according to their assigned study arm at baseline, regardless of adherence to study protocol. Modern per protocol analyses will also be conducted to estimate treatment effects for participants who adhered to the protocol. All analysis results will be two-tailed, with a significance level at 0.05 and 95% confidence intervals.

All measures will be analyzed using mixed effects modeling, followed by generalized estimating equations to account for irregularly spaced measurements, fully utilizing all repeated measures and all available data. Missing data will be imputed using multiple imputation and likelihood-based analyses. Case analysis or single

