imputation methods may also be used and a specific approach for imputation will be selected based on key attributes of the obtained data, including % missing and whether data are missing at random^109. Sensitivity analyses will be conducted to determine if data are missing at random. In these analyses, allowing for random intercepts and slopes, the change (slope) will be the key dependent variable and the randomization status will be the key independent variable. The results of these analyses can be easily converted to group or treatment differences at post assessments. In our mixed effects modeling, all variables will be analyzed as continuous with the exception of clinical concerns (occurrence/non-occurrence), which will be treated as a repeatedly measured binary outcome.

As an exploratory investigation, multiple variables will be investigated as possible moderators of treatment effects on depressive symptoms (PHQ-8). For example, we may evaluate medication status, symptom severity, age, sex, COVID19 specific factors, and aspects of program engagement (e.g., time to complete program, duration of use) as potential moderators. For this investigation, we will employ the MacArthur framework for moderator analysis, following the eligibility and analytical criteria for determining moderators. To maximize power, moderator analyses will also be conducted using mixed effects modeling.

Exploratory analyses using mixed effects modeling will also be conducted to evaluate whether successive program updates (between versions 2 and 3 of Limbix Spark) result in statistically significant differences on primary and secondary outcome measures, including depressive symptoms, global functioning, and treatment adherence, usability, and engagement.

Content analysis of post-study interviews will be conducted. Data will be codified to identify themes with an emphasis on engagement, usability, comprehension, therapeutic alliance, and overall impact of treatment. Key insights will be drawn from themes and contextualized with quantitative user session data.

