Lastly, we will assess treatment adherence by evaluating treatment-related differences in rates of program completion and daily mobile app usage using independent samples (between treatment and control groups) or paired (within the educational control group) t-tests. We will also assess treatment-related differences in self-reported usability and engagement using the SUS and UES scales descriptively by comparing means and variability between groups and within group (control group only)

Statistical analyses for the primary outcome variable and between group differences in rates of clinical concerns rates will be conducted when N=60 (~30/grp) and N=120 (~60/grp) participants have completed Phase II. If no statistical differences are detected in the primary outcome variable, possible moderators of treatment status on the primary outcome may be evaluated, including age, concurrent treatment, and PHQ-8 score at baseline. Results of the interim analyses may be used to adjust recruitment targets for the remainder of the trial.

An effect size will be calculated for the primary outcome and may be used to determine sample size for a Phase III trial.

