#### **4.5 Data Monitoring**

This is a low risk research study.

A clinical concern is defined here as any negative experience or symptom reported by participant or parent in the Participant Symptom Check Questionnaire, in freeform text, spontaneously reported, or clinically significant deterioration of symptoms, whether or not thought to be associated with participation in the study.

Clinical concerns will be categorized as follows:

0- Not a clinical concern: Research team determined that triggering event was not a clinical concern

1- Mild clinical concern: Research team determined that triggering event doesn't require clinician input and will continue to monitor participant's responses

2- Moderate clinical concern: Research team determined that triggering event requires clinician input. Clinician determined that research team should continue to monitor participant's responses but that no follow-up was needed.

3- Elevated clinical concern: Research team determined that triggering event requires clinician input. Clinician determined follow-up was indicated and confirmed participant safety (participant did not endorse intent to self harm) via email or phone communication with participant or their parent/guardian or their provider.

4- Significant clinical concern: Research team determined that triggering event requires clinician input. Clinician determined that follow-up was indicated and after follow-up with participant, parent/guardian, or provider determined that participant should be withdrawn from study (e.g. due to suicide attempt, self-harm or self-harm attempt, suicidal ideation with intent, reported hospitalization for self-harm or suicide attempt while enrolled in study).

All adverse device effects and complaints will be recorded (whether anticipated or unanticipated). The project PI and study clinician will determine whether it is in the participant's best interest to remain in the study after any clinical concern.

Anticipated serious clinical concerns, given the study population, include depressive symptoms as defined in the DSM-V, suicidal ideation, active self-harm, clinically significant deterioration in depressive symptoms, suicide attempts, and suicide.

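### Phase II makes its choice of imputation depend partly on establishing MAR, which observed data cannot do, and plans no analysis of departures from MAR for the primary PHQ-8 result

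*Combined protocol and SAP*

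**What the plan says.** All of this is in section 4.4 (Data Analysis), Phase II, unless noted.

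- Main model: "The core analysis strategy in this project is longitudinal mixed effects modeling", fitted by maximum likelihood to all repeated measures.
- Missing data: "Missing data will be imputed using multiple imputation and likelihood-based analyses". Case analysis and single imputation are allowed as further options. No particular form is named, and they are not described as supportive only.
- Choice of method: "a specific approach for imputation will be selected based on key attributes of the obtained data". Two attributes are listed: the proportion missing, and whether MAR holds. The sentence cites a published guide to multiple imputation in trials.
- Purpose of the sensitivity analyses: "Sensitivity analyses will be conducted to determine if data are missing at random". No test, criterion or alternative scenario follows.

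The primary outcome (section 4.1, Phase II) is the between-group difference in PHQ-8 change from baseline to 5 weeks in participants with baseline PHQ-8 of 10 or more. Section 2.1 assumes 27% attrition.

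Two rules elsewhere can create missing scores. Under section 3.1, participants who report a "change in their treatment for a mental health disorder while enrolled in the study, they may be withdrawn from the study". Under section 4.5, the highest grade of clinical concern is one where the clinician "determined that participant should be withdrawn from study". On withdrawal, "access to the web portal and mobile app will be restricted at that time". By section 3.4, the portal and the app are the two routes by which PHQ-8 is collected.

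**The concern.** MAR and MNAR differ only in how the unseen values relate to the seen ones. The data can show how much is missing, and can show that missingness is related to recorded variables, which contradicts MCAR. They cannot show that nothing further depends on the unseen scores. A rule that waits for that answer before choosing an imputation approach therefore cannot be followed as written, and in practice the choice would be left to judgement after the data have been seen.

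The larger consequence is what is left out. The mixed model and multiple imputation, in standard form, both rest on MAR. The only sensitivity analyses planned for missing data are directed at establishing that assumption, not at relaxing it. No delta-adjusted, pattern-mixture, selection-model, reference-based or tipping-point analysis appears anywhere in the document. A reader of the Phase II result could not learn how much worse the unseen Spark scores would have to be before the conclusion changed.

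**Working it through.** **1. The plan's own figure.** Section 2.1 gives 175 for d = 0.5, 80% power, two-sided 0.05 and 27% attrition. A two-sample t-test needs 63.8, so 64 per arm, 128 in total; 128/0.73 = 175.3. With 175 × 0.73 = 127.75 completers, power is 80.1%. The figure reproduces. It implies 175 × 0.27 ≈ 47 participants without the outcome.

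**2. Can MAR be determined?** I simulated a standardised outcome with 27% missing and moved only the unseen values by 0, 0.5 and 1.0 SD. The observed mean stayed at −0.002 and the correlation of response with baseline at 0.001 in all three cases. The full-data mean moved from 0.00 to 0.13 and 0.27, that is, by 0.27 × shift. The observed data are identical under every shift, so no test based on them can detect it.

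**3. How large a departure would matter?** This is an illustration, not the planned analysis.

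Inputs: d = 0.5 and 27% missing (section 2.1); equal arms (section 3.1); 175 randomised, or a minimum of 120 recruited (section 2.1), or "N=120 (~60/grp) participants have completed Phase II" (section 4.4). Assumptions of mine: SD of change 5, range 4 to 6, because the documents give none, so the effect is 0.5 × 5 = 2.5 points; 27% missing in each arm; a t-test on week-5 change.

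Let δ be the average number of points by which unseen Spark scores are worse than MAR predicts, and kδ the same for controls. Then

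- estimate = 0.5·SD − 0.27·δ·(1 − k)
- SE² = 2·SD²/n_obs + 0.27·0.73·δ²·(1 + k²)/n
- significance is lost where estimate/SE = t(0.975, 2·n_obs − 2)

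Here n is randomised per arm and n_obs is observed per arm: 88 and 64 for 175 randomised; 82 and 60 for 120 completing; 60 and 44 for 120 randomised.

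Worked case, 120 randomised, k = 0, δ = 1.39: estimate = 2.5 − 0.27 × 1.39 = 2.125; SE = √(50/44 + 0.1971 × 1.39²/60) = 1.069; ratio 1.988, the critical value on 86 df.

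| Scenario | p at δ = 0 | Tipping δ, k = 0 (SD 4 to 6) | Tipping δ, k = 0.5 (SD 5) | p if δ = 2.5, k = 0 |
|---|---|---|---|---|
| 175 randomised | 0.005 | 2.7 (2.2–3.3) | 5.0 | 0.043 |
| 120 completing | 0.007 | 2.5 (2.0–3.0) | 4.6 | 0.050 |
| 120 randomised | 0.021 | 1.4 (1.1–1.7) | 2.6 | 0.093 |

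With k = 1 and equal missingness the estimate does not move.

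As a cross-check, holding the SE at its completers' value gives a one-sided tipping point of 0.56 SD with 175 randomised (2.8 points at SD 5) and 0.28 SD with 120 randomised (1.4 points).

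**4. Dependence on the amount missing.** By the same simpler calculation with 175 randomised and only Spark shifted, the tipping shift is 1.85 SD at 10% missing, 0.83 SD at 20%, 0.56 SD at 27% and 0.28 SD at 40%.

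**The case against.** The plan's main method is a sound one. Weekly PHQ-8 scores enter the mixed model, and clinical-concern withdrawals will often follow something already recorded: a rising PHQ-8, a symptom check or free text. Missingness that depends on recorded scores in the model is MAR. A reader might infer from the withdrawal rules that dropout is informative and the primary estimate therefore biased. The documents do not support that: the rules make some informative dropout possible, and the weekly scores absorb part of it. Withdrawal for a treatment change is also partly a separate question, since section 4.4 already allows those participants' data to be left out of the primary analysis, and a delta adjustment would not settle that.

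The illustration is not the planned slope model, and it is one-sided in its main column. A week-5 PHQ-8 may be in the app even when the portal assessment is missed, so 27% attrition need not mean 27% missing primary data. Two of the three one-sided scenarios need unseen Spark scores to lose at least the whole assumed effect before significance goes. These limits all stand. They bear on how fragile the result might be, not on whether MAR can be determined.

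A reader might also infer that allowing single imputation makes the p-value too small. That does not follow. The plan names no such method, its wording reads most naturally as an addition to the main analyses, and the effect on error rates depends on which form is used; carrying the last score forward, for example, need not inflate the error rate.

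The cited guide may contain more detail on choosing a method. Its content is not in the document, and no guide can make MAR verifiable from observed data. Finally, section 3.1 says Phase II may not be powered, and section 2.1 reserves a powered study for Phase III. That lowers the weight of the point. It does not remove it, because Phase II has an effectiveness primary outcome tested at 0.05.

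**Conclusion.** The point holds as a specification fault with two parts. One criterion for choosing the imputation approach cannot be applied, and no analysis of departures from MAR is named for the primary PHQ-8 result. Neither part depends on the numerical assumptions.

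The size is conditional. If only Spark dropouts are worse than MAR predicts, the margin is roughly the whole assumed effect with 175 randomised or 120 completing, and about 56% of it (1.39/2.5) with 120 randomised. The margin nearly doubles if missing controls shift half as much. All of this rests on an observed d of 0.5, 27% missing in each arm, an assumed SD and a week-5 t-test; a smaller observed effect would tip sooner. The tipping points should not be read as a finding that the Phase II result is fragile, nor the point as a fault in the mixed model or the sample size. The plan gives no means of finding out how robust the result is, and it should be amended to do so.

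**What to change.** In section 4.4, Phase II:

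1. Delete the sentence on determining MAR, and remove MAR status as a criterion for choosing the imputation approach.
2. State that the maximum likelihood mixed model on all observed PHQ-8 scores is primary under MAR whatever missingness is found, with multiple imputation that uses the weekly scores as its check.
3. Add a prespecified delta-adjusted tipping-point analysis by multiple imputation. Shift the imputed PHQ-8 values separately by arm, for example from 0 to 5 points (up to twice the assumed 2.5-point effect). Report the estimate and confidence interval at each step and where significance is lost.
4. Label case analysis and single imputation as supportive only.

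The cost is a few sentences and a few hours of analysis. Sample size and study procedures do not change. The downside is that the team gives up the freedom to switch method after seeing the data.

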### **3.4 Assessments**

Baseline and post-intervention assessments for participants and parents (if under 18) will be completed via a secure web portal. Weekly participant assessments will be completed in the mobile app. Weekly parent assessments will be completed via secure web portal.

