## Schedule of Assessments:

|  | Baseline | Weekly during study | Post-intervention |
|--|----------|---------------------|-------------------|
| Patient Health Questionnaire (PHQ-8)                   | X        | X                   | X                 |
| Baseline Questionnaire- Participant                    | X        |                     |                   |
| Baseline Questionnaire- Parent                         | X        |                     |                   |
| Brief Resilience Scale                                 | X        |                     |                   |
| Generalized Anxiety Disorder (GAD-7)                   | X        |                     | X                 |
| PROMIS Pediatric Global Health Scale                   | X        |                     | X                 |
| PROMIS Parent Proxy Global Health Scale                | X        |                     | X                 |
| Mood and Feelings Questionnaire (Short Parent Version) | X        |                     | X                 |
| Participant Symptom Check- Participant                 |          | X                   |                   |
| Participant Symptom Check- Parent                      |          | X                   |                   |
| Post Program Questionnaire- Participant                |          |                     | X                 |
| Post Program Questionnaire- Parent                     |          |                     | X                 |
| System Usability Scale                                 |          |                     | X                 |
| User Engagement Scale                                  |          |                     | X                 |

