## Description of Assessments

- The **Patient Health Questionnaire (PHQ-8)** is an 8-item self-report measure for screening for depression and for establishing depression severity. The PHQ-8 has been demonstrated to have high sensitivity and specificity in both adolescents and young adults. Clinically significant improvement is defined as a reduction in assessment score  $\geq 5$ . Post-intervention scores  $< 10$  are defined as remission.
- **Baseline Questionnaire- Participant and Parent:** Contains demographic, clinical history questions, and questions related to the impact of COVID-19.
- The **Brief Resilience Scale** is a 6 item self-report measure for assessing the ability to “bounce back” or recover from stress. It has been shown to be reliable and to measure a unitary construct.
- **7 item Generalized Anxiety Disorder scale (GAD-7).** The GAD-7 is a brief 7-item assessment for generalized anxiety disorder with satisfactory sensitivity and specificity. We will evaluate changes in anxiety symptoms given the high comorbidity between anxiety and depression.

- **PROMIS Pediatric Global Health Scale and PROMIS Parent Proxy Global Health Scale:** The PROMIS Pediatric and Parent Proxy Global 7+2 are 9-item measures that produce essentially a unidimensional measure of global health perception/well-being.
- **Mood and Feelings Questionnaire Short Parent version (MFQ-PS).** The MFQ-PS consists of a series of 13 descriptive phrases regarding how the subject has been feeling or acting recently and is a screening tool for depression in children and young people.
- **Participant Symptom Check- Participant & Parent.** Assesses parent and participant reported clinical concerns, severity level, and relationship of the clinical concern to the intervention.
- **Post-Program Questionnaire- Participant and Parent.** Contains questions about changes in treatment and questions about COVID19
- **System Usability Scale (SUS).** Provides a “quick and dirty”, reliable tool for measuring the usability of systems. It consists of a 10 item questionnaire with five response options for respondents; from Strongly agree to Strongly disagree. The SUS has become an industry standard, with references in over 1300 articles and publications. It is a very easy scale to administer to participants, can be used on small sample sizes with reliable results, and is valid – it can effectively differentiate between usable and unusable systems.

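### Phase II: a random-slope change model does not suit four scales measured twice or binary remission, and leaves baseline handling unstated

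*Combined protocol and SAP*

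**What the plan says.** Section 4.4 (Data Analysis, Phase II) sets the general method: "All measures will be analyzed using mixed effects modeling, followed by generalized estimating equations to account for irregularly spaced measurements". It then gives the form of the model: "In these analyses, allowing for random intercepts and slopes, the change (slope) will be the key dependent variable", with randomised arm as the key independent variable. It adds that the results convert readily to group differences at the post assessment. On outcome type it says that in the mixed models "all variables will be analyzed as continuous with the exception of clinical concerns (occurrence/non-occurrence"). On missing values: "Missing data will be imputed using multiple imputation and likelihood-based analyses".

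The Schedule of Assessments marks the PHQ-8 at baseline, weekly and post-intervention. The row "Generalized Anxiety Disorder (GAD-7") is marked at baseline and post-intervention only, as are the PROMIS Pediatric, PROMIS Parent Proxy and short parent MFQ rows. Section 3.4 agrees: "Baseline and post-intervention assessments for participants and parents (if under 18) will be completed via a secure web portal".

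Remission is a secondary outcome in sections 1.1 and 4.2 (Phase II). Under Description of Assessments, post-intervention PHQ-8 scores below 10 "are defined as remission". Section 4.4 also says "All analyses will be restricted to those participants with PHQ-8" of at least 10, unless otherwise indicated.

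Section 4.4 gives adherence its own t-tests and treats SUS and UES descriptively. It names no separate method for the four two-visit scales or for remission. It mentions neither a baseline covariate nor a common baseline mean.

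**The concern.** Two features of the stated model do not fit the data it will receive.

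- **Four scales with two visits.** Two measurements per person cannot separate a random slope from residual error. The practical question is how baseline is handled. A model with arm-specific baseline means and one with a common baseline mean both fit the text, but they have different standard errors. If the choice is open, it can be made after the data are seen.
- **Remission.** This is one yes/no value per person at the end of treatment. A pre-to-post slope has nothing to work on at baseline, and no binary method is named. Baseline PHQ-8, a likely predictor of crossing 10, would go unused.

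At stake is precision on secondary outcomes, using data already collected.

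**Working it through.** **The plan's own figure.** Section 2.1 gives 175 for d = 0.5, 80% power, two-sided 0.05, a t-test and 27% attrition. The t-test needs 63.77, so 64 per arm, and 128/0.73 = 175.3. The figure reproduces and is not in dispute.

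**Inputs**
- 44 per arm: the Phase II minimum of 120 less 27% (section 2.1), 120 × 0.73 / 2 = 43.8.
- 60 per arm: the 120 completers of the second planned analysis (section 4.4).
- Baseline-post correlation r = 0.3 / 0.5 / 0.7 and equal SDs at both visits: assumed, as the documents give none.
- Yardstick 0.5 SD: the top of the 0.3 to 0.5 range that the Phase I part of section 4.4 calls clinically significant.

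**Step 1: identification.** Let D11, D12 and D22 be the random-effect variances and covariance and s² the residual variance, with visits at 0 and T.
- Var(baseline) = D11 + s²
- Cov = D11 + T·D12
- Var(post) = D11 + 2T·D12 + T²·D22 + s²

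Three equations hold four unknowns. The Jacobian has rank 3 of 4 at weeks 0 and 5, and 4 of 4 at weeks 0 to 5, the PHQ-8 schedule. With time coded 0 and 1, variances of 1 and covariance 0.5 are reproduced exactly by residual variance 0, 0.1, 0.2, 0.3 or 0.4 paired with slope variance 1.0, 0.8, 0.6, 0.4 or 0.2. All give the same total covariance, so the treatment estimate and its standard error do not depend on which is chosen.

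**Step 2: where arm enters.** Generalised least squares at two visits, SD 5, r = 0.5:

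| Arm enters | SE, 44 per arm | SE, 60 per arm | Equals |
|---|---|---|---|
| Intercept and slope | 1.066 | 0.913 | Change score |
| Slope only | 0.923 | 0.791 | ANCOVA |

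**Step 3: size.** In SD units with n per arm, SE² = 4(1−r)/n for the change score and 2(1−r²)/n with baseline adjustment. The ratio is (1+r)/2 = 0.65 / 0.75 / 0.85. Its square root is 0.81 / 0.87 / 0.92, so the interval is 19% / 13% / 8% narrower at any n. The detectable difference at 80% power is 2.80 × SE. Power is by normal approximation.

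| | r = 0.3 | r = 0.5 | r = 0.7 |
|---|---|---|---|
| Detectable, 44 per arm: change v adjusted (SD) | 0.71 v 0.57 | 0.60 v 0.52 | 0.46 v 0.43 |
| Detectable, 60 per arm (SD) | 0.60 v 0.49 | 0.51 v 0.44 | 0.40 v 0.37 |
| Power for 0.5 SD, 44 per arm | 51% v 69% | 65% v 77% | 86% v 91% |
| Power for 0.5 SD, 60 per arm | 64% v 82% | 78% v 89% | 94% v 97% |

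Parent scales cover only participants under 18, a share not given. If it is half (assumed), n is 22 or 30 per arm. At r = 0.5, power for 0.5 SD then goes from 38% to 48%, or from 49% to 61%.

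**Step 4: remission.** Everyone analysed starts at PHQ-8 of 10 or more, so the indicator is 0 at baseline and its change equals its post value. A linear model therefore returns the raw difference in proportions, which is unbiased but unadjusted.

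Simulation assumptions: 4,000 trials per cell; baseline PHQ-8 10 to 24 (mean 15.8, SD 3.5); post SD about 5; effect 2.5 points; remission about 30% v 49%; realised correlations 0.29 / 0.49 / 0.69. The standard error of the risk difference, adjusted over unadjusted, was 0.976 / 0.923 / 0.830 at 44 per arm and 0.980 / 0.932 / 0.826 at 60. A rerun gave about 0.99 / 0.93 / 0.83. The mean risk difference was 0.19 both ways. Power rose from 44 / 45 / 45% to 46 / 51 / 58% at 44 per arm, and from 57 / 58 / 59% to 59 / 65 / 73% at 60.

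**The case against.** - **The random-slope fault does no harm by itself.** This stands. The effect is estimable and unbiased whichever variance split the software reports, and the GEE in section 4.4 needs no random slope. A reader might infer that the four comparisons are invalid or cannot be fitted; the documents do not support that.
- **Actual times could restore identification.** Section 3.1 allows two weeks for the post assessments, and section 4.4 expects irregular spacing. With actual times such as 5, 5.5, 6 and 7 weeks the rank is 4 of 4. The claim therefore holds for nominal visits. With spread times the components are identified, but only weakly.
- **The literal text may lose nothing.** Arm is tied to the slope and no arm term in the intercept is mentioned. Read that way, the model already matches ANCOVA. But an arm main effect is common practice and nothing excludes it. The 8-19% is conditional, and the range starts at zero.
- **It is not one model for everything.** This stands: GEE is added, and adherence, SUS and UES have other methods. The sentence on random slopes also follows one on missing-data sensitivity analyses. Its reference to randomised arm and post differences favours the main-model reading.
- **Remission may simply be unaddressed.** A reader might infer that the plan orders remission to be modelled as continuous. It can equally be seen as a rate derived from the PHQ-8 on which the plan is silent. Either way, no suitable method is named.
- **The inputs are assumed, and Phase II may be underpowered by design (section 3.1).** True. Only r is varied; the remission scenario is a single case. At 64 per arm and r = 0.5 even the change score gives SE √(2/64) = 0.177 and about 81% power for 0.5 SD.

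**Conclusion.** The point holds in a limited form. For GAD-7, both PROMIS scales and the parent MFQ, the random-slope components cannot be identified at two nominal visits, and the baseline handling that decides the standard error is unstated. A common baseline mean or ANCOVA gains 19% / 13% / 8% in interval width at assumed r = 0.3 / 0.5 / 0.7 if arm would otherwise enter the intercept, and nothing if it would not. Remission needs a binary method at post-intervention. Baseline adjustment brings about 0-2% / 7% / 17% off its standard error in the illustrated case.

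A reader might infer a threat to the primary result. The documents do not support that: the weekly PHQ-8 identifies the random slope, and this point does not affect the primary conclusion. Baseline handling is equally unstated for the PHQ-8, but the two-visit figures here do not apply to it. This is a worthwhile precision improvement to secondary outcomes, not a correction of bias.

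**What to change.** In section 4.4 (Phase II):

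1. For GAD-7, PROMIS Pediatric, PROMIS Parent Proxy and the parent MFQ, specify a two-visit model with unstructured covariance, a common baseline mean across arms and no random slope. The alternative is ANCOVA of the post value on arm and baseline value, with the multiple imputation already named.
2. Add remission to the binary exception. Analyse it at post-intervention by logistic regression on arm and baseline PHQ-8, using the same imputation, and report a standardised risk difference with 95% confidence interval.

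The cost is wording only, with no new visits, data or participants; it should be settled before outcome data are seen by arm. The small downside is that ANCOVA drops participants without a post value unless they are imputed. The common-baseline model keeps them.
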